8.3.4. Secondary analysis

All secondary endpoints will be summarized by timepoint (see section 7.3 for details) using appropriate descriptive statistics as detailed above. 95% two-sided confidence intervals will also be calculated for the frequency and mean estimates at each timepoint, as appropriate. Time to event endpoints will be assessed using Kaplan-Meier curves.

Specific details of the analysis of each secondary endpoint, including the rules for handling missing values, will be provided in the SAP.

8.3.5. CIP deviations

Major CIP deviations are deviations from the CIP which potentially could have a meaningful impact on study conduct, or on the primary or secondary outcomes for an individual subject. The criteria for identifying major CIP deviations will be defined within the appropriate CIP-specific document at study start. Major CIP deviations will be reviewed as part of the ongoing data cleaning process and all-important deviations will be identified and documented prior to database lock to confirm inclusion or exclusion from analysis sets. The analysis will be conducted on the FAS.

CIP deviations will be summarized for all deviations and by type, with event counts and number of subjects with at least one deviation.

8.3.6. Subgroup analysis

Analyses will be performed to investigate potential differences in primary and secondary outcomes between, but not limited to, the following baseline groups:

1. Individual subjects, vessel or lesion characteristics defining procedures of increased complexity.
2. Gender (female/male).
3. Age (<75 years/≥75 years).
4. Vascular access site (radial/femoral/other).

8.4. Sample size

Target recruitment of 500 patients.

8.5. Missing Data

There will be imputation for missing data. Partial dates may be handled as follows: if the day is missing then it will be imputed as 1, if the month is missing it will be imputed as January. Missing years will not be imputed.

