3.2. Study duration

The total expected duration of the study is approximately 36 months.

Enrollment will take place over a period of 18 months. Follow up is planned for 12. There will be an additional 6 months for data freeze, core lab analysis and statistical analysis.

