3.3.2. Secondary Endpoints

1. Individual components of TLF at 1 month and 1 year.
2. Minimum stent area (MSA) measured at the end of the index procedure.
3. Strategy success defined as:
 - Successful stent delivery
 - $\geq 80\%$ stent expansion

- Complete stent apposition
- No edge dissection
- Full lesion coverage with <50% plaque burden at proximal and distal references
- TIMI 3 flow
- 4. Target vessel revascularization (TVR)
- 5. Target lesion revascularization (TLR)
- 6. Stent thrombosis
- 7. Stroke
- 8. Cardiovascular death
- 9. Acute kidney injury
- 10. Major bleeding, categorized as class 3-5 according to the Bleeding Academic Research Consortium [BARC]
- 11. Procedure time
- 12. Fluoroscopy time
- 13. Radiation exposure (dose-area-product)
- 14. Cost effectiveness analysis

4. Study Population

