5.7. Follow-up

Follow-up assessment visits will be at the following intervals following the index procedure:

- Hospital discharge
- 30 days (\pm 1 week)
- 12 Month (\pm 1 month)
- Unscheduled visit

The following assessments and information will be collected at all follow-up visits:

- Review of concomitant medications including antithrombotic medications
- Endpoint collection
- Adverse event assessment/reporting

In addition to above assessments, for the **12-month follow-up** the following assessments will need to be performed as well:

- Physical examination
- Review of laboratory data
- 12-lead ECG

All follow-up time-points, except for 12-month time-point for which the subject needs to attend the clinic, may be completed by phone call (or if standard hospital practice during an office visit).

A summary of required follow-up procedures is listed in Table 1.

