8.3. Statistical analyses

8.3.1. General considerations

The study design aim is to validate a comprehensive, IVUS guided calcium modification algorithm for moderate to severely calcified coronary lesions and its effects on the primary and secondary outcomes outlined in section 3.3 herein. As such, no statistical hypothesis has been formulated

Proprietary and Confidential - Property of CVRI Dublin, Ireland

in accordance with the single arm, observational design. Descriptive statistics and graphical displays will be used to summarize the study findings and outcomes.

Continuous variables will be summarized by the number of observations, arithmetic mean, standard deviation (SD), median, minimum, maximum and interquartile range unless otherwise stated. For categorial variables, frequency tables will be produced including counts and percentages. Time to event variables will be assessed using Kaplan-Meier curves. There will be no imputation of missing values, unless otherwise described in the statistical analysis plan.

Estimates will be provided with corresponding two-sided 95% Confidence Intervals. No adjustments will be made for multiple testing.

Continuous variables will be reported as mean and standard deviation or median and interquartile range, as appropriate. The distribution of continuous variables will be assessed by the Shapiro-Wilk test. Categorical variables will be reported as counts and percentages and compared by Pearson χ^2 or Fisher exact test, as appropriate. In general, the denominator for the percentage calculation will be based upon the number of non-missing values available, unless otherwise specified.

For time-to-event analysis other than the primary endpoint for the de-novo patients, Kaplan-Meier survival curves as well as confidence intervals based on the log-log transformation will be reported.

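### The day-1/January rule for partial dates in 8.5 has no lower bound at the index procedure, and 8.5 contradicts 8.3.1 on whether missing data are imputed

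*Protocol*

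**What the plan says.** Protocol section 8.5 opens with "There will be imputation for missing data". It continues "Partial dates may be handled as follows" and gives the rule: "if the day is missing then it will be imputed as 1, if the month is missing it will be imputed as January". It closes with "Missing years will not be imputed". It does not say which dates the rule covers, and it does not require the result to fall on or after the index procedure.

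Section 8.3.1 says the opposite about imputation in general: "There will be no imputation of missing values, unless otherwise described in the statistical analysis plan".

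Event dates are used in several places:
- Section 3.3.2 lists "Individual components of TLF at 1 month and 1 year" as the first secondary endpoint.
- Sections 8.3.1 and 8.3.4 call for Kaplan-Meier curves for time-to-event endpoints.
- Appendix A divides stent thrombosis into timing classes that start at 0-24 hours.
- Section 8.3.3 analyses the co-primary TLF endpoint as a binary proportion at 1 year with an exact interval.

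**The concern.** A day set to 1 and a month set to January can leave a date unchanged or make it earlier, never later. For medical history that is harmless. For an event after PCI it can give a date before PCI, which is impossible. Such an event has a negative time on a Kaplan-Meier curve and fits none of the stent-thrombosis timing classes. The same backward pull can turn an event after day 30 into a 1-month event, and one just after day 365 into a 1-year event.

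The two statements on imputation raise a separate problem. A reader of 8.5 alone could expect a missing MSA or TLF status to be imputed; a reader of 8.3.1 would not. The exception in 8.3.1 is for what the SAP describes, and 8.5 is protocol text, so the exception does not reconcile them.

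**Working it through.** The protocol gives no figure on this point: no expected share of partial dates and no expected TLF rate. There is nothing to reproduce, so the check applies the rule literally.

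**Inputs from the protocol.** The rule (8.5); enrolment over 18 months, about 548 days (3.2); reading points at 1 month and 1 year (3.3.2); a 12-month visit with a window of plus or minus 1 month (5.7), so events on about days 366-395 can be reported.

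**Assumptions.** Index dates uniform over the 548 days; event days uniform within the stated range; enrolment starting on the first of each of the 12 calendar months in turn. Month missing means that day and month are both missing, so the date becomes 1 January. Every share below is a share of partially dated events.

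**Hand check, day missing.** The imputed date precedes PCI when the event falls in the same calendar month as PCI and PCI was not on the 1st. For PCI on day k of a month of L days, L - k later days remain in that month. Averaging over k, for events in days 1-30:
- L = 31: (0 + 1 + ... + 29) / (31 × 30) = 435 / 930 = 46.8%
- L = 30: (0 + 1 + ... + 28) / (30 × 30) = 406 / 900 = 45.1%

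For events over 365 days: 435 / (31 × 365) = 3.8% and 406 / (30 × 365) = 3.7%. The largest possible shift is 30 days (from the 31st to the 1st), so no event after day 30 can land before PCI.

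**Hand check, month missing.** The imputed date precedes PCI when the event falls in the same calendar year as PCI and PCI was not on 1 January. Over one full year of enrolment: (0 + 1 + ... + 363) / 365² = 66,066 / 133,225 = 49.6%. Eighteen months of enrolment weights one half of the calendar year twice, so the share depends on the starting month.

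**Full enumeration** (every index date crossed with every event day; range over the 12 starting months):

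| Result | Day missing | Month missing |
|---|---|---|
| Days 1-30, dated before PCI | 46% | 94-97% |
| Days 1-365, dated before PCI | 3.8% | 41-58% |
| Days 31-365, dated before PCI | 0% | 37-54% |
| Days 31-365, moved into days 0-30 | 4.4% | 6-11% |
| Days 366-395, moved to day 365 or earlier | 49% | 94-97% |
| Mean backward shift, days 1-365 | 14.7 days | 182 days |

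If half of all events occur in the first 30 days, the day-missing share dated before PCI is about 0.5 × 46% + 0.5 × 0% = 23%.

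**Absolute scale.** The protocol does not give the rates needed, so these are assumed: 500 patients, 1-year TLF of 5-15%, and 2-10% of event dates partial.
- Partially dated TLF events: 500 × 0.05 × 0.02 = 0.5 up to 500 × 0.15 × 0.10 = 7.5.
- Dated before PCI, day missing, uniform events: 0.5 × 0.038 = 0.02 up to 7.5 × 0.038 = 0.3.
- Dated before PCI, day missing, half of events early: 0.5 × 0.23 = 0.1 up to 7.5 × 0.23 = 1.7.
- Dated before PCI, month missing, uniform events: 0.5 × 0.41 = 0.2 up to 7.5 × 0.58 = 4.4.

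**Would a floor at the index date be enough?** It removes every date before PCI but not the window error. With the month missing, day 31-365 events that were dated before PCI would move to day 0. Added to those already moved into days 0-30, 45-63% of day 31-365 events would count as 1-month events. With only the day missing, about 4% still would.

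**The case against.** The rule is permissive: 8.5 says partial dates may be handled this way. Sections 8.1 and 8.3.4 leave technical detail, including missing-value rules for secondary endpoints, to the SAP, which could add a lower bound. The affected endpoints are also those least likely to carry partial dates. Endpoint events are adjudicated by the CEC (11.1, 14.3), adverse event forms record the onset date (5.12), and serious events are to be reported within 3 calendar days of occurrence or awareness (6.2.1). A missing month, which drives the large percentages, should be rare for a death, infarction or revascularization. The opening sentence of 8.5 may simply have lost the word no.

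Most of this stands, and it limits the size of the point. It does not remove it: the protocol states this rule and no other, and the rule gives impossible dates when followed. Partial dates remain possible, because no contact is scheduled between day 30 and month 12. A lost word is plausible but cannot be confirmed from the text.

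A reader might infer more than the document supports:
- That many follow-up events will be misdated. Only partially dated events are touched, and their number is not given.
- That a missing month usually puts the event before PCI. That is secure for first-month events; over the year it is about half.
- That back-dated events will be lost. No passage says that events with negative times are dropped. Section 6.1 excepts unchanged pre-existing events from the adverse event definition, but it does not govern how adjudicated endpoints are analysed.
- That the co-primary result is compromised. Binary 1-year TLF changes only if an event is excluded as pre-index or a late event is pulled inside 1 year.

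**Conclusion.** The point holds as a minor one, in two parts.

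First, the rule in 8.5, applied to post-procedure events, can produce dates before PCI and wrong window assignments. The shares in the table rest on uniform enrolment over 18 months and uniform event times, and they apply only to partially dated events. The number of those is unknown. Under the assumed rates it is between 0.5 and 7.5 TLF events, of which at most about 4 would be dated before PCI, and usually far fewer. The effect is therefore on individual events in the 1-month and 1-year TLF components, the stent-thrombosis timing classes and the Kaplan-Meier curves.

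Second, 8.5 and 8.3.1 contradict each other on imputation. This needs no assumption, and the two statements must be reconciled.

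**What to change.** 1. Limit the day-1/January rule to medical-history dates.
2. For post-procedure events, require the imputed date to be no earlier than the latest of (a) the first day of the known month or year, (b) the index procedure and (c) the last documented event-free contact, and no later than the contact at which the event was reported.
3. Have the SAP say where between these limits the date is placed. A date set exactly at an event-free contact held on or before day 30 would still read as a 1-month event. The midpoint is one acceptable convention for a missing month, not a requirement. Where the limits straddle day 30 or day 365, the known information cannot settle the window, so the SAP should state how such events are counted and report their number.
4. Replace the opening sentence of 8.5 with one that agrees with 8.3.1: no imputation other than of partial dates, unless the SAP specifies it.

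The cost is a few sentences in 8.5 and the SAP. No further data collection is needed, since contact dates and onset dates are already recorded.

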9. DATA COLLECTION, HANDLING AND RETENTION

9.1. General

Data will be managed as per EU General Data Protection Regulation (GDPR 2016/679).

9.2. Source Document Verification (SDV)

Source document Verification (SDV) for this study will be maintained to capture the course of treatment and to substantiate the integrity of the trial data. SDV will include, but is not limited to, worksheets, hospital and/or clinic or office records documenting subject visits including study and other treatments or procedures, medical history and physical examination information, imaging results, device accountability records, medical consultations and laboratory results and reports.

9.3. Electronic Data Entry

When using electronic data handling or remote electronic trial data systems, the Sponsor or the Sponsor's representative will:

- Ensure and document that the electronic data processing system(s) conforms to the Sponsor established requirements for completeness, accuracy, reliability, and consistent intended performance (i.e., validation).
- Maintain SOPs for using these systems.
- Ensure that systems are designed to permit changes to the data in such a way that the data changes are documented and there is no deletion of any edited or entered data (i.e., maintains an audit trail).
- Maintain a security system to prevent unauthorized access to the data and to uniquely identify individuals who access the data entry system.
- Maintain a list of individuals authorized to make data changes.
- Maintain adequate data backup.

Primary data collection based on source-documented hospital and /or clinic chart reviews will be performed clearly, timely, adequately, and accurately by site personnel trained on the protocol and eCRF completion. Sponsor or designee will perform clinical monitoring as specified in Monitoring Plan.

1.1. Data Confidentiality and Data Protection

A role concept with personal passwords (site investigator, statistician, monitor, administrator etc.) regulates permission for each user to use the system and database as he/she requires.

All data entered into the CRFs are transferred to the database. Each data point has attributes attached to it identifying the user who entered it with the exact time and date. Retrospective alterations of data in the database are recorded in an audit table. Time, table, data field and altered value, and the person are recorded (audit trail). Images collected are encrypted.

9.4. Study Records Retention

All eCRF information, study records, reports and Source Documents (SD) that support the eCRF must be retained in the files of the responsible investigator for a minimum 7 years following notification by the Sponsor or designee that all investigations have been completed and will further be retained in accordance with local and international guidelines as identified in the Investigator Site Agreement.

The core laboratory will also maintain study records. They will maintain study records until the Sponsor notifies them that research is completed/terminated under the clinical investigation in compliance with national law. All study data will be archived for a minimum of 7 years after study termination or premature termination of the study.

10. REPORTING

10.1. Annual Progress Report

Annually, as requested by independent ethics committee (IEC) or national regulations.

10.2. End of Study Report

The investigator should notify the IEC in writing within three months after completion, termination, or discontinuation of the study at the site. The same procedure will be applied to regulatory authorities where required.

10.3. Other Reporting

The reporting requirements of the investigator also include, but are not limited to:

- Inform the Sponsor of IEC approval withdrawal.
- Major deviations from the clinical study protocol to the Sponsor
- Report or ensure the reporting, to the IEC by the Principal Investigator(s) as required by national regulations or the clinical study protocol or by the IEC.

11. MONITORING, QUALITY CONTROL AND ASSURANCE

11.1. Site Monitoring Plan

The investigators will allow onsite inspection of subjects' SD as requested by the Sponsor or required by an IEC or regulatory authorities. Monitoring activities may take place at the trial center or any ancillary facility where study conduct takes place. The investigators will provide access to all SD and adequate workspace. The investigators will be available to the Sponsor, IEC, or other regulatory authorities to discuss study issues as requested.

Sites will be initiated and trained on the clinical study requirements. Assurance of the accuracy and reliability of data will consist of checking the consent forms and consent process, on site and remote monitoring. All required data for this study will be collected into an eCRF. Appropriate computer editing programs will be run to verify the accuracy of the data.

There will be 100% informed consent verification, and all primary and secondary endpoint events up to 1 year will be adjudicated by an independent Clinical Events Committee (CEC). Verification of other SD will be performed as specified in the monitoring plan.

Data monitoring will occur at the Sponsor's discretion and in all cases where data irregularities are identified. As needed, intermittent monitoring visits may be conducted to compare data entered into the database to the subjects' SD.

Further details are outlined in the Monitoring Plan.

11.2. On-site Audits

The investigators will allow on-site inspection of subjects' SD as requested by the Sponsor or required by an IEC or regulatory authorities. Monitoring activities may take place at the trial center or any ancillary facility where study conduct takes place. The investigators will provide access to all SD and adequate workspace. The investigators will be available to the Sponsor, IEC, or other regulatory authorities to discuss study issues as requested.

If an Investigator is contacted by a Regulatory Agency in relation to this clinical trial/investigation, the Investigator will notify the Sponsor immediately and EC as appropriate.

11.3. Protocol Deviations

Investigators are not allowed to deviate from this CIP without prior authorization by the Sponsor except under emergency situations when necessary to preserve the rights, safety or well-being of study subjects.

Deviations and non-compliances will be recorded together with an explanation. Deviations or non-compliances that impact the rights, welfare, or safety of subjects shall be reported as soon as possible to the Sponsor and IEC, as required.

If appropriate, corrective, and preventive actions will be discussed by the Sponsor, investigator, and/or the IEC to determine a suitable course of action.

Deviations include, but are not limited to the following list:

- Failure to receive assigned treatment.
- Failure to obtain informed consent prior to conducting study specific activities.
- Inclusion/exclusion criteria not met.
- Incorrect version of the CIP/PIL used.
- Subject could not be reached for a follow-up visit or follow-up visit was outside window.
- AEs not reported by investigators in the required timeframe as specified in the protocol.
- Source data permanently lost.

Site compliance regarding deviations will be reviewed by the clinical study manager on a regular basis. In addition, all deviations from the protocol will be documented in the final report.

11.4. Protocol Amendments

Investigators will not modify, change, or otherwise amend the protocol without prior written consent of the Sponsor. As applicable, if a protocol amendment substantially alters the scientific validity of the study or affects the subjects' rights, safety, welfare, or their willingness to continued participation in the study, the subject should generally be re-consented on an updated and approved (as required by local law and regulation) ICF. New procedures or processes which substantially alter the scientific validity of the study or affects the subjects' rights, safety, welfare, or their willingness to continued participation the study will not be implemented until an approval or favorable opinion has been granted by the reviewing IEC, as applicable.

11.5. Core Laboratory

Two independent core laboratories will be used to perform quantitative coronary analysis (QCA) and intravascular ultrasound (IVUS) imaging analysis at:

- Baseline for the index procedure
- Post-calcium modification
- Post-PCI for all subjects
- Endpoints requiring a re-PCI in the treated lesion.

12. More details can be found in the study specific Core laboratory Plan.ETHICS AND REGULATORY

12.1. Regulation statement

This protocol has been developed and the study will be run in accordance with the ethical principles that have their origin in the Declaration of Helsinki (2013). [1] Further the study will be run in compliance with ISO 14155 (2nd edition) 2011. Both investigators and Sponsor will conduct this study in accordance with any applicable local or regional laws and regulations. Investigators will neither conduct procedures specific to the study nor collect subject data without prior approval or favorable opinion of any IEC under whose jurisdiction the conduct of this study falls. It is acknowledged that in some geographic areas IEC review and approval of study data collection activities may not be required.

During the conduct of study activity, the investigators and the Sponsor shall act in accordance with any further requirements as imposed by an IEC or regulatory agency.

